7.1 Study Schedule of Events	
7.2 Blood Collection Schedule	

1. Objectives

We hypothesize that IMM-124E, a bovine colostrum enriched with anti-LPS antibodies, will improve insulin resistance and decrease systemic and hepatic inflammation through modulation of bacterial products and the microbiome in pediatric NAFLD.

1.1 Primary Objective: The principal objective of this blinded, placebo-controlled, pilot study is to evaluate whether 12 weeks of IMM-124E in children with NAFLD in combination with standard of care (SOC) will decrease inflammation in the liver as measured by ALT. Specifically, percent change in ALT from Week 0 to Week 12 in treatment compared to placebo.

1.2 Secondary Objectives:

- To assess the safety and tolerability of IMM-124E in children with NAFLD
- To assess the effects of IMM-124E on secondary and exploratory endpoints:
 - Mean change in ALT in treatment group compared to placebo
 - Fasting glucose and insulin
 - Hemoglobin A1C
 - o Adipo-IR
 - Oral glucose tolerance test
 - NAFLD pediatric diagnostic panel
 - Fasting plasma lipids
 - Stool microbiome
 - Blood transcriptomics
 - Systemic inflammation (cytokines)
 - Metabolomics
 - Visceral Adiposity (AMRA MRI scan)
 - Hepatic fat percent (AMRA MRI scan)
 - o BMI z-score
 - Waist circumference
 - Depression
 - Quality of life
 - Composite endpoint of "metabolic improvement" specified as > 10% improvement in TG/HDL ratio, improvement in insulin resistance, and >10% improvement in ALT

2. Background and Significance

Nonalcoholic fatty liver disease (NAFLD) is an aggressive, obesity-associated chronic liver disease that affects ~7 million children in the US (10% of all children) and is one of the top 3 indications for liver transplant in adults. Currently, the only treatment available for NAFLD is lifestyle advice to decrease adiposity and improve insulin sensitivity but this is rarely effective. It is our long term goal to improve the health of children by understanding how to prevent, treat and cure NAFLD. In our previous studies, we demonstrated that children with NAFLD have endotoxemia as well as systemic inflammation. Further, individuals with NAFLD have a disturbed microbiome (dysbiosis) and increased gut permeability. Thus, the mechanism of NAFLD is thought to include chronic inflammation from intestinal microbiome-derived

products (lipopolysaccharide (LPS) and metabolites) which pass through the "leaky gut" to the liver where they activate the innate immune response.

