IMM-124E is a hyperimmune colostrum-derived product from cows inoculated with bacterial products from 13 strains of *E. coli*. Preliminary data suggests that IMM-124E improves insulin sensitivity, reduces liver inflammation and promotes regulatory T cells that suppress chronic inflammation. IMM-124E acts at the level of the mucosa in the gut by improving barrier function and decreasing systemic exposure to microbial products (LPS). It could also alter the gut microbial populations by targeting pathogenic bacteria (*E. coli*). IMM-124E is being tested in adults for treatment of NAFLD and alcoholic hepatitis under 2 separate FDA approved INDs. A similar product is sold over-the-counter in Canada and Australia. IMM-124E is considered a medical food and *little is known regarding its potential use in children*. It is important to study in children because the NAFLD histology is different compared to adults. Waiting for the results of adult trials will have little benefit for children. The objective of this proposal is to evaluate the preliminary effectiveness, safety and mechanisms of action of IMM-124E in children with NAFLD.

In this proposal, we will test the following central hypothesis: IMM-124E, a bovine colostrum enriched with anti-LPS antibodies, will improve insulin resistance and decrease systemic and hepatic inflammation through modulation of bacterial products and the microbiome in pediatric NAFLD. The aims of this study are the following:

- To determine if a 3-month treatment with IMM-124E in combination with standard of care lifestyle advice (SOC) is safe and results in greater improvement in 1) hepatic inflammation (alanine amino transferase - ALT) 2) insulin sensitivity 3) blood lipids in children with NAFLD compared to placebo with SOC as well as safety related endpoints.
- 2. To define mechanism of action related endpoints in response to 3 months of IMM-124E in children with reduction in the above outcomes including: stool microbiome (16S rRNA), metabolomics, intestinal inflammation (stool calprotectin), systemic inflammation (cytokines), transcriptomics (immune response) and correlate these with changes in clinical measurements.

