We will test our hypothesis and accomplish the aims through a randomized, double-blind, 3 month treatment trial of children age 6-19 years with a diagnosis of NAFLD by biopsy or MRI. IMM-124E and placebo will be provided by Immuron. Patients will be recruited from the Children's Healthcare of Atlanta pediatric liver clinical practice which cares for over 400 pediatric NAFLD patients and has an extensive record of successful clinical trials in children. The sample size of 40 participants is powered for change in ALT as the primary outcome and allows sufficient power for subgroup analysis and secondary outcomes. High resolution, high throughput metabolomics will be combined with transcriptomics of PBMCs, 16S rRNA characterization of the stool microbiome to determine gut-level and system-level response to IMM-124E.

These studies are designed to inform decision making about the design of a future large, multicenter trial testing IMM-124E. We will leverage our position as members of the NIH supported clinical research network (NASH CRN) in which pediatric investigators are eager to conduct a phase III trial of IMM-124E if

the data shows promise. These studies have great potential to advance progress towards a new therapeutic for NAFLD, thus improving health for millions of children.

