3.9 Potential Risks

There is minimal risk in these studies. Potential risks are related to 1) blood draws, 2) NPO status, 3) cumulative blood loss 4) IMM-124E side effects and 5) confidentiality.

- The placement of an intravenous catheter and drawing of blood specimens has minimal risk of discomfort, bruising, or bleeding. There is minimal risk of infection or extravasation. Experienced staff with pediatric expertise will place all catheters and draw blood.
- 2) Patients will remain NPO from the midnight of the morning of the study until the fasting portion of the study is concluded. Fasting will be done before the Week 0 (Baseline) and Week 12 visits. Some children may become agitated with NPO status. Water will be encouraged to maintain hydration. Each participant will be asked to drink one glass of

water at bedtime prior to the study and one glass in the morning before leaving home for the research center.

- 3) Blood loss: To minimize risk to the patient, we will carefully monitor the total blood required for the 4 study visits and stay well within the NIH clinical center guidelines recommending less than 3ml/kg at a single research visit and no more than 7ml/kg over any 6 week period. See Table 2 for blood collection schedule and amounts.
- 4) Patients will be taking a concentrated milk protein product. It is possible that it could cause GI symptoms including nausea, diarrhea, gas, bloating or pain. Participants will be monitored for incidence and severity of gastrointestinal events.
- 5) There is risk of loss of confidentiality. Efforts will be made to keep all personal information confidential. All data will be stored in locked offices and password-protected computers. Personal identity will be protected in any publication.

Alternative treatments and procedures: New information on NAFLD diagnosis or new treatments for NAFLD in children may become available over the study period. This information will be incorporated into these studies and alternate diagnosis or treatment methods may be substituted if more appropriate. They will continue in the study if they desire and lab information from the study will be made available to their physician if requested.

3.10 Protection Against Risks:

Recruitment and Informed Consent

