Subjects may be approached by the research team about the study either in person in clinic or over the telephone. A verbal consent will be obtained at this time if the subject is interested in scheduling a screening visit. The patient will be instructed to not have anything to eat or drink (except plenty of water) for 12 hours prior to the scheduled research visit. They will also be made aware of the risks associated with fasting (feeling lightheaded or agitated). If the screening window is anticipated to be shorter than usual (based upon the patients schedule etc) then the study team may need to collect a 24-hour dietary recall during the screening period prior to the initial screening visit (where the patient first signs the informed consent document). This procedure is also detailed in the verbal consent. A member of the study team will call the subject on the telephone and will ask them what they have had to eat and drink in the last 24 hours.

If the patient is approached about the study in clinic and chooses to screen during their appointment then the verbal consent will not be required if the subject is already fasting for intended SOC labs.

Participants who sign consent/assent documents will be registered in study and assigned a study number. If the participant does not meet eligibility criteria or meets all the eligibility but decides not to continue in the study before randomization at Week 0 he or she will be deemed a screen failure. A screening log will be kept to track all screening activities and reasons for screen failures. As described above, a patient may be screened a second time if they desire this and the reason for failure is likely to have resolved in the opinion of the investigator.

Screening procedures will be performed as indicated in the Study Schedule of Events (Attachment 1). Recording of any patient information will not begin until informed consent and assent has been obtained. The screening visit will take place within six weeks of the randomization date, Week 0.

Screening visit (up to - 6 weeks)

Pre-screening activities such as chart review of standard of care labs or referral from a colleague will identify potential participants for screening. If the participant is deemed eligible he or she along with a legal guardian will sign the consent/assent documents before or during the screening visit.

After informed consent is obtained the following procedures will be conducted at the screening visit:

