4.3 Follow-up Visits

Participants will be required to return to the study site at Weeks 6 and 12. Each study visit will have a visit window of ±5 days, although the ideal visit date will fall on the exact anniversary date from randomization. Procedures to be performed at these visits can be seen in Attachment 1 (Schedule of Events).

The study assessments to be completed at each visit are outlined below:

Week 6 visit:

- Collection of vitals (including blood pressure, respiratory rate, heart rate, and body temperature)
- Anthropometric assessments (including height, weight, waist and hip circumference)
- Review of concomitant medications and adverse events
- Drug accountability assessment
- Drug dispense from research pharmacy
- laboratory assessments (see Blood Collection Schedule- Attachment 2 for more detail)
- Stool sample collection
- Blood spot collection

Week 12 visit:

- Administration of 3, 24-hour recalls (NDS-R) prior to visit
- PROMIS Questionnaires
- Physical Examination
- Collection of vitals (including blood pressure, respiratory rate, heart rate, and body temperature)
- Anthropometric assessments (including height, weight, waist and hip circumference)
- Review of concomitant medications and adverse events
- Drug accountability assessment
- 2-hour oral glucose tolerance test
- Participant counseling regarding follow-up care
- Fasting laboratory assessments (see Blood Collection Schedule- Attachment 2 for more detail)
- Stool sample collection
- Blood spot collection
- MRI
- Optional Sub-study: Accelerometer data collection for 1 week (prior to Week 12 visit)

Optional Sub-study: Accelerometers

An optional sub-study will be presented to subjects at the time of consent. Participation in this sub-study will be optional and will not be required if subjects are participating in the main study. Actigraph GT3X accelerometers will be given to subjects at the Baseline visit and prior to the Week 12 visit. Study staff will place the accelerometer around the subject's waist over the right hip and instruct them on how to properly replace the equipment after showering. Phone calls will be made to remind the subjects as needed. Subjects will collect 7 consecutive days of data and will bring the device back with them to their next appointment or mail the equipment back in prepaid mailers. A phone interview will be performed at the end of each monitoring period to record any unusual activity or episodes of removal.

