4.5 Specimens

Plasma samples are all collected in EDTA tubes and plasma is separated within two hours of the blood draw. The samples are aliquoted into tubes and immediately frozen and stored at -80 C. Stool will be stored at -80 C. We will use the Nautilus software, by Thermo Scientific, which is a central laboratory information management system (LIMS) service provided by the ACTSI and Emory research laboratories. The systems facilities the tracking and management of specimens, laboratory inventories, and reagent ordering; the management of lab and QC data; the acquisition of data directly from instruments; and the exchange of laboratory results data. This will allow us to easily store and retrieve samples for future analyses.

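### PBMCs are drawn only at screening, so the planned PBMC transcriptomic response to IMM-124E has no sample taken after randomisation

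*Combined protocol and SAP*

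**What the plan says.** Three places treat transcriptomics as a measure of response to treatment.

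- Section 1.2 puts blood transcriptomics in the list headed "To assess the effects of IMM-124E on secondary and exploratory endpoints". The synopsis also lists it.
- Aim 2 in section 2 is "To define mechanism of action related endpoints in response to 3 months of IMM-124E in children with reduction in the above outcomes". Its list of endpoints includes transcriptomics as an immune-response measure, to be correlated with changes in clinical measurements.
- The design summary in section 2 names the specimen: "transcriptomics of PBMCs, 16S rRNA characterization of the stool microbiome to determine gut-level and system-level response to IMM-124E".

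The sampling plan is in Attachment 2 (section 7.2). Its PBMC row has 8 mL at screening, blanks at Week 0, Week 6 and Week 12, and a row total of 8 mL. On timing, section 4.1 says "The screening visit will take place within six weeks of the randomization date, Week 0". The visit lists in sections 4.1 and 4.3 and the Schedule of Events (Attachment 1) refer to Attachment 2 for blood work and add no PBMC collection.

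**The concern.** A response to treatment needs at least one sample taken on or after treatment. The only PBMC sample here precedes randomisation. It can support a baseline description, or an analysis of whether initial expression predicts later clinical change. It cannot show what IMM-124E does to PBMC gene expression, and no analysis method can recover that afterwards.

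At stake is an exploratory endpoint and the transcriptomic part of Aim 2, in a pilot that section 2 says is meant to inform a larger multicentre trial. Serum, plasma and stool are all collected at Weeks 0, 6 and 12, so PBMCs stand out as the specimen with no on-treatment collection.

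**Working it through.** **1. Reproduce the plan's totals.** Inputs are the rows of Attachment 2, in mL, with blanks and dashes taken as zero.

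| Row | Screening | Week 0 | Week 6 | Week 12 | Total |
|---|---|---|---|---|---|
| Metabolic panel | 4 | 4 | 4 | 4 | 16 |
| Serum | 0 | 6 | 6 | 6 | 18 |
| Plasma | 0 | 12 | 6 | 12 | 30 |
| OGTT | 0 | 9 | 0 | 9 | 18 |
| Sum without PBMCs | 4 | 31 | 16 | 31 | 82 |
| Printed total | 12 | 31 | 16 | 31 | 90 |
| Difference = PBMCs | 8 | 0 | 0 | 0 | 8 |

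The printed totals are reproduced with PBMCs at screening only.

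**2. Could a cell have shifted in the PDF?** An 8 mL draw can be present or absent at each of four visits, which gives 2^4 = 16 patterns. Compared with the printed visit totals, only screening alone matches. Week 12 alone, for example, would give 4/31/16/39, and screening plus Week 12 would give 12/31/16/39 = 98.

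**3. Could another specimen fill the gap?** Section 4.5 says "Plasma samples are all collected in EDTA tubes and plasma is separated within two hours of the blood draw" and then describes aliquoting and freezing; it does not mention recovering cells. PBMCs also have their own row, apart from plasma. "Blood spot collection" is listed at Weeks 0, 6 and 12, but no purpose is given and nothing links it to RNA.

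**4. Is a post-treatment tube feasible?** Section 3.9 sets the limits: "less than 3ml/kg at a single research visit and no more than 7ml/kg over any 6 week period". Section 3.6 gives weights of 50 to 120 kg in the group's earlier paediatric trials. Assume the same 8 mL tube, moved from screening to Week 0 and repeated at Week 12:

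- Visit totals: 12 − 8 = 4; 31 + 8 = 39; 16; 31 + 8 = 39. Sum = 98 mL, against 90 now.
- Largest single draw: 39 mL. 39/3 = 13, so the single-visit limit is met above 13 kg. At 50 kg, 39/50 = 0.78 mL/kg.
- Largest six-week total: screening, Week 0 and Week 6 can fall within 42 days if screening is at most 5 days before Week 0 and Week 6 is 5 days early (5 + 37 = 42). Now: 12 + 31 + 16 = 59 mL. Revised: 4 + 39 + 16 = 59 mL, unchanged. 59/7 = 8.4, so the limit is met from about 8.4 kg. At 50 kg, 59/50 = 1.18 mL/kg.
- Week 6 plus Week 12: 16 + 31 = 47 mL now, 16 + 39 = 55 mL revised, still below 59.

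**The case against.** The mismatch and the arithmetic are hard to dispute. The better arguments concern weight and scope.

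- **It is a small part of a pilot.** Transcriptomics is one item in a long secondary and exploratory list, is absent from the secondary endpoints in section 5.2, and has no dedicated analysis in section 5.4. This stands, and it limits the importance of the point. It does not remove the conflict, because the synopsis and section 1.2 both still list the endpoint.
- **Only one sentence says PBMCs.** Section 1.2 and Aim 2 name no specimen, so the blood spots might be intended. This stands as a condition: what is shown is the loss of the PBMC measure. No text assigns RNA work to the blood spots, so for now the wider endpoint has no identified post-treatment specimen.
- **Section 4.5 is weak evidence.** It omits serum handling too, although serum is drawn at three visits. That is fair; the finding rests on Attachment 2 and its totals.
- **Aim 2 focuses on responders and correlation.** A between-arm comparison answers section 1.2 more directly than Aim 2. Also true, but a measure of response to three months of treatment still needs a later sample.
- **The tube need not move.** Keeping screening and adding only Week 12 also totals 98 mL (12/31/16/39) and allows a between-arm comparison. Correct: the Week 12 tube is essential, and the move to Week 0 is an improvement.

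**Conclusion.** The concern holds. As scheduled, 0 of 40 children have a PBMC sample after randomisation, so neither within-child change nor a between-arm effect on PBMC expression can be estimated. The one sample available may predate the first dose by up to six weeks.

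This rests on reading the blank cells as no collection, which the printed totals confirm, and on no unstated specimen supplying the cells. The documents do not show whether the table or the text is in error. The primary ALT analysis and the other scheduled endpoints are not affected. It should be fixed, because a listed endpoint cannot be delivered on PBMCs as written and the remedy is cheap.

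**What to change.** Reconcile sections 1.2 and 2 with Attachment 2 in one of three ways.

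1. **Add the sample (preferred).** In Attachment 2, move the 8 mL PBMC tube from screening to Week 0 and repeat it at Week 12, giving 4/39/16/39 and a total of 98 mL. Add PBMC handling to section 4.5. In section 5.4, state that Week 12 expression is compared between randomised arms with adjustment for Week 0, and keep the Aim 2 correlations as a separate exploratory analysis. A lighter variant keeps the screening tube as baseline and adds only Week 12, for the same 98 mL.
2. **Name another specimen.** If the blood spots or another tube are meant to supply RNA, say so in section 4.5 and correct the PBMC wording in section 2.
3. **Relabel.** If no post-treatment sample is feasible, describe transcriptomics in the synopsis, section 1.2 and Aim 2 as a baseline predictor and drop it as a response endpoint.

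Option 1 costs 8 mL more blood per child at existing visits, processing and assay of about 40 more samples (45 with the approximately 5 extra enrolments in section 3.5), and a short amendment. The screening draw falls from 12 to 4 mL, so children who fail screening give 8 mL less. Option 3 needs text changes only.

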3.4 Rescreening

If a potential participant fails screening due to a changeable criteria such as acute illness, use of a supplement or anti-oxidant, and ALT < $2 \times ULN$, the participant may rescreen a second time if they desire to after a reasonable amount of time has passed and if the investigator thinks the participant is likely to qualify the second time.

3.5 Treatment Groups:

Characteristics: 40 children age 6-19 years from any ethnic and racial categories will be included. Males and females will be recruited equally, however because of the increased prevalence of NAFLD in adolescent boys compared to girls, we may enroll more boys. In order for 40 children to complete the protocol, we will over-enroll at baseline by approximately 5 additional participants to allow for dropout.

NAFLD Patient Eligibility: Children ages 6-19 will be included because NAFLD typically presents around age 10, although sometimes at a young age. Young adults, age >19 years, will not be included because their travel for school and work makes participation more difficult. For NAFLD, each patient must meet the typical criteria for diagnosis including typical clinical and laboratory changes of NAFLD and liver biopsy or MRI consistent with NAFLD. If the subject only has had an ultrasound they may have their baseline MRI conducted up to 2 weeks prior to confirm the diagnosis. Subjects with 5% or more liver fat on their MRI will meet entry criteria and can proceed with the study. Other chronic liver disease must have been ruled out using a serologic work-up.

3.6 IMM-124-E Administration:

Dose and Frequency: IMM-124E is a medical food and has a wide range of potential dosing. The dose recommended by Immuron is 20 mg/kg. Previous trials for adults have ranged from 600 - 3,600 mg/day and the tablets range from 200 - 450 mg each. Because IMM-124E is very safe and well-tolerated, our goal is to provide the most effective dose without the major burden of taking pills. In our previous pediatric NAFLD trials, the weights have ranged from 50 kg to 120 kg. Because of this, we will use the recommended adult dose of 600 mg 3 x daily. To facilitate compliance the IMM-124E is provided as a dried powder with flavoring. At the time of consuming, the powder is mixed with a small amount of water and then the child/teen drinks it. Administration instructions will be provided and standardized for the trial. An example of this is participants will be asked to take the product (or placebo) before breakfast (preferably on an empty stomach and about 30 minutes before eating), afterschool or in the afternoon (before snacking) and at bedtime (corresponds to 3 times per day).

Storage and record keeping of the IMM-124E and placebo will be performed by the research pharmacy of the ACTSI and Children's Healthcare of Atlanta.

Manufacturing of Placebo: Placebo will be prepared from cow's milk protein concentrate (PROMILK 85) purchased by Immuron from Tatura Industries in Australia. The milk protein is certified for human consumption and is typically used to make ice cream, yogurt, cheese, and other milk products. All of the milk sourced for PROMILK 85 is from Australian dairy cattle which is similar to the source of IMM-124E. The placebo packets will look and taste similar to IMM-124E and have similar dairy fat and micronutrient content. The lactose content of the placebo is higher but this is unavoidable. Because of this, lactose

intolerant children will be excluded. Lactose content will be standardized across all the placebo packets used in the study.

3.7 Recruitment and Retention Strategies:

Our research team has years of experience recruiting and retaining children into research studies at Emory University and Children's Healthcare of Atlanta. We have a large network of recruitment sites and many families that have expressed interest in participating in future studies. From our current database of participants who have previously participated in our protocols, we have already identified over 50 eligible individuals who could be approached to participate in this study. In addition, new patients with evidence of NAFLD from Children's Healthcare of Atlanta hepatology clinics, and referring centers/practices may be considered as candidates. It is our experience that approximately 50 new cases of children who have liverbiopsied NAFLD can be identified each year from the Children's liver clinics. We will continue to use our proven retention strategies, including scheduling children on weekends and school holidays (to minimize missing school), completing visits early in the morning (to allow return to school), contact after visits to ensure participant satisfaction with visits, child-friendly facilities and providing entertainment during longer visits (movies, video games, etc).

3.8 Sources of Materials:

The sources of research material obtained will include blood specimens, medical records, imaging results and data collection forms used to record data during the study. Participants will complete the Block Physical Activity Questionnaire to record current activity level during the study. The survey will be performed at baseline. Participants will be asked to maintain their current level of activity. Nutrition data will be collected by telephone or in person in the form of triple pass 24-hour recalls prior to randomization and again before the final study visit. Phone calls will be used to assess tolerability and compliance with the product. Specimens and data will be obtained and recorded both as part of routine medical care and for research purposes. Only study personnel (PI, co-Is, study coordinator, research assistant and nutritionist) will have access to identifiable data. Data will be de-identified before analysis. Data will be stored in locked research material cabinets and on password-secured databases on the Emory network.

